4 PARTICIPANT ENTRY

4.1 Study population

(i) Inclusion criteria

- 1. Aged 18 or above
- 2. *Ventricular Ejection Fraction (EF) ≤ 40%; BNP needs to be ≥250ng/L for patients with EF 36-40%,
- 3. New York Heart Association (NYHA) class II-IV
- 4. **PR interval ≥200ms
- 5. **Narrow QRS duration (≤140ms) or prolonged QRS duration with typical Right Bundle Branch Block (RBBB) morphology on 12 lead ECG and sinus rhythm

* Ejection Fraction should be based on patient's echocardiograph within the last 18 months; if that is not available a new echo will be performed. Patients with EF 36-40% must have at least one BNP result within the last 18 months having a value of \geq 250ng/L, otherwise, a blood test will be done to assess BNP. Some centres use NT-pro BNP test instead of BNP. An NT-pro BNP result of \geq 600ng/L is acceptable.

** ECG criteria should be based on patient's ECG within the last 18 months; if that is not available a new ECG will be performed.

(ii) Exclusion criteria

- 1 ***Permanent or persistent atrial fibrillation (AF)
- 2 Paroxysmal atrial fibrillation with history of sustained AF (more than 24 hours) in the 6 months prior to screening
- 3 Patients who are unable to perform cardiopulmonary exercise testing
- 4 Other serious medical condition with life expectancy of less than 1 year
- 5 Lack of capacity to consent

HOPE-HF Sponsor: Imperial College (study ref: 15HH2828)

- 6 Pregnancy (female participants of reproductive age will be eligible for inclusion in the study, subject to a negative pregnancy test prior to randomisation)
- 7 Contraindication to use of the relevant study device or leads (as per current manuals from manufacturer)

***Patients who have persistent AF in their medical history but has then resolved can be included.

Eligible patients can be sub-divided into 2 groups: A) patients who do not have an indication for an implantable ICD (this group will receive His CRT-P); and B) patients who do have an indication for an implantable ICD (this cohort will receive His CRT-D)

Patients who meet the study inclusion criteria, but have completed other research studies or concurrently participating in a non-interventional study (e.g. observational studies) may be invited to take part in the trial at the Investigator's discretion.

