5 PROCEDURES AND MEASUREMENTS

5.1 Screening and pre-randomisation evaluations

Written informed consent will be obtained before the subject undergoes any screening procedures.

Potential study participants will be identified following the review of medical notes of patients attending; general cardiology clinics, Heart Failure clinics, ICD clinics or during admission to hospital. Patients who potentially fulfil the study inclusion criteria and none of the exclusion criteria will be identified and approached by members of their direct healthcare team to discuss study participation.

All subjects will be assigned a study-specific subject number at the screening visit and the following tests/assessments will be performed:

- 1. ECG (can be taken at the visit or within the past 18 months; this ECG determines patient eligibility and will be reviewed centrally)
- 2. Echocardiography (new echo will be performed if no report is available within the past 18 months)
- 3. BNP or NTproBNP in some centres (sample is only taken for patients with EF 36-40% and have no available BNP result within the past 18 months).
- 4. Demographics
- 5. Medical History
- 6. Physical Examination
- 7. Pregnancy test will be performed for women of childbearing age

Eligible patients will be asked to complete a resource utilisation questionnaire at this visit.

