5.5 Study assessments

Physical examination

Patients will have a physical examination where vital signs will be taken.

Cardiopulmonary exercise testing:

Patients will exercise on a treadmill using a "smoothed modified Bruce" protocol ³⁰. A physiologist and another HOPE HF study team member (e.g. research nurse, research fellow or another physiologist) will be present for this test. For safety reasons, it is necessary to perform ECG monitoring during this test. It may be possible to see pacing spikes in the ECG. Therefore to ensure that the physiologist who is leading the exercise test is blinded, the screen displaying the ECG will only be visible to the second study personnel who will be responsible for monitoring ECG. They will only request that a test is stopped if there are ECG findings which make this necessary on clinical safety grounds. This way both the patient and the physiologist leading the exercise test will remain blinded to the treatment arm. Exercise capacity will be measured as peak exercise oxygen consumption in ml/kg/min.

BNP:

We will take 5mls of blood to measure B type Natriuretic Peptide (BNP) in an EDTA bottle. The samples will be analysed at the Hammersmith hospital and no sample will be stored.

Echocardiography:

Patients will have a standard HOPE HF echo protocol performed including left ventricular dimensions, volumes, ejection fraction and quantification of mitral regurgitation. No ECG will be recorded during the echocardiogram once the patient is randomised. The physiologist performing the test will be blinded to the treatment arm.

Daily Activity Measurement:

All implanted devices in the study can provide data on daily activity measured in minutes per day. The comparison will be made between the His pacing and no His pacing arms.

Quality of Life (QOL) and Cost Effectiveness Evaluation questionnaires:

The economic evaluation will compare incremental costs and incremental outcomes of the direct His-bundle pacing against standard medical care. The economic evaluation will consist of two parts, a cost-effectiveness analysis (CEA) and a cost utility analysis (CUA). In the CEA the incremental cost-effectiveness ratio (ICER) will be expressed as the incremental costs per point improvement in exercise capacity in peak VO₂. The primary outcome measure in the CUA will be Qualitative Adjusted Life Years (QALYs), based on the EuroQoL EQ-5D scores.

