The analysis will be based on an intention-to-treat (ITT) principle. The comparability of the groups, in both costs and outcomes, will be examined by a baseline analysis. When both groups are not comparable methods will be applied to control for these differences. Normal distribution of the costs and effects will be tested by Kolmogorov-Smirnov test. When the normal distribution is not present, non-parametric bootstrapping will be performed to analyse the differences between the intervention and control group. The bootstrap method will be used to calculate the 95% confidence intervals (CI). The incremental cost-effectiveness ratio (ICER) will be based on the incremental costs and incremental effects of the intervention group and the control group and will be calculated as followed: ICER = $\Delta costs/\Delta$ effects. $\Delta costs$ and Δ effects are respectively the differences in costs and effects of the intervention and control group. Within the cost-effectiveness analysis the ICER will be expressed as costs per outcome rate and within the cost-utility analysis, the ICER will be expressed as the costs per QALY gain. A cost-effectiveness plane will be plotted with bootstrapped ICERs.

iv) Sub-group Analysis

- 1) Around 30% of patients (40 patients) recruited into the study are expected to have right bundle branch block. We will perform subgroup analysis to determine if the magnitude of haemodynamic response to AV optimised direct His bundle pacing is of a similar magnitude to that obtained in patients with narrow QRS duration.
- 2) We will perform analysis to determine whether a change in peak V0₂ and the haemodynamic response is related to baseline PR interval.
- 3) We will perform analysis to determine whether a change in peak VO2 and the haemodynamic response is related to E-A fusion as observed by baseline echocardiography.
- 4) We will perform analysis to determine the effect of AV delay optimised His Bundle pacing on daily activity level compared to control measured objectively in minutes per day by the CRT device.
- 5) If there are significant numbers of patients with non-selective His capture (where both the His and local ventricular myocardium are captured by the pacing stimulus) then we will perform subgroup analysis to determine whether there is a difference in the magnitude of either acute haemodynamic or change in peak V0₂.

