- 6) If there are significant numbers of patients who are implanted with an LV lead due to the failure of His lead implantation we will perform subgroup analysis to determine whether there is a difference in their haemodynamic and peak VO2 response

compared to their control state and compared with the successful His implanted lead cohort.

- 7) A sub-group analysis will be performed to investigate patients recruited with a Ventricular Ejection Fraction of 35% and below against those recruited with an EF or greater than 35% for primary and secondary endpoints. Where possible, the analysis will be stratified by PR Interval in order to investigate whether PR is a predictor for treatment response.
- 8) It is anticipated that the vast majority of patients will have an indication for an implantable ICD. In the event where there is an even split between the two groups, an additional exploratory analysis may be carried out on the trial outcomes, using indication group as an additional stratification factor.
- 9) We will perform an analysis to assess the relationship between pacing device effect (in terms of change in peak VO2 and haemodynamic response) and BMI.

9 **REGULATORY, ETHICAL AND LEGAL ISSUES**

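### Sub-group item 7 studies ejection fraction as an effect modifier only through a 35% split of recruitment EF; adding a continuous EF interaction from the visit 3 echocardiogram would use the data better

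*Protocol*

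**What the plan says.** Item 7 of the sub-group list in Protocol section 8.2 compares "patients recruited with a Ventricular Ejection Fraction of 35% and below against those recruited with an EF or greater than 35" per cent, for the primary and secondary endpoints. It adds: "Where possible, the analysis will be stratified by PR Interval in order to investigate whether PR is a predictor for treatment response".

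On which EF this is, section 4.1 says "Ejection Fraction should be based on patient's echocardiograph within the last 18 months", and section 5.1 says a "new echo will be performed if no report is available within the past 18 months". Section 4.1 caps EF at 40% and sets a further condition for the upper band: "BNP needs to be ≥250ng/L for patients with EF 36-40" per cent. An NT-proBNP of at least 600 ng/L is accepted instead.

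The trial echocardiogram in section 5.5 covers "left ventricular dimensions, volumes, ejection fraction and quantification of mitral regurgitation". Appendix 2 schedules it at visits 3 (randomisation), 4 and 5.

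Other modifiers are worded as relationships with no stated cut. Item 2, for example, asks whether change in peak VO₂ and the "haemodynamic response is related to baseline PR interval"; item 9 does the same for BMI.

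**The concern.** Item 7 is the only place where the plan asks whether response depends on EF, and it asks by comparing two groups. Three features weaken the answer.

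- **The cut.** EF is continuous and capped at 40%, so the upper group covers only 36-40% and may be small. Splitting it further by PR makes the cells smaller still.
- **The EF value.** On its natural reading, the EF patients were recruited with is the eligibility EF. It may be much older than the visit 3 value, which is taken after a run-in without His pacing and before treatment.
- **BNP selection.** Patients above 35% had to meet a natriuretic peptide threshold and those at or below it did not. A difference between the groups could reflect either EF or BNP.

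The risk is one of interpretation: a null result from a small, selected group could be reported as no difference by EF.

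**Working it through.** **1. The plan's own figure.** Section 8.1 gives a difference of 0.7, SD of the paired difference 2.4, two-sided alpha 0.05 and power 90%. The normal approximation is (1.96 + 1.28)² × 2.4² / 0.7² ≈ 123.5. The exact paired t calculation gives 126 (power 0.901). Then 126 / (1 − 0.21) = 159.5, so 160. Both figures reproduce, and 126 and 2.4 are used below. The protocol gives no EF mean, SD or share above 35%, and no sub-group power.

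**2. Age of the EF.** Up to 18 months at screening, plus 2 to 6 months from screening to randomisation (Appendix 2), gives up to 18 + 6 = 24 months at randomisation. What this costs in precision cannot be worked out from the protocol.

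**3. What the two-group contrast can detect.** This needs only the share p above 35%, not a shape for the EF effect. SE = 2.4 × √(1/(126p) + 1/(126(1−p))). The detectable difference at 80% power is (1.96 + 0.84) × SE.

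| p (assumed) | patients above 35% | SE | detectable difference, ml/kg/min |
|---|---|---|---|
| 10% | 13 | 0.71 | 2.0 |
| 20% | 25 | 0.53 | 1.5 |
| 30% | 38 | 0.47 | 1.3 |
| 50% | 63 | 0.43 | 1.2 |

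For 10-30% above the cut this is 1.3/0.7 = 1.9 to 2.0/0.7 = 2.9 times the effect for which the whole trial is sized. If a PR split halved the upper group (an assumption; no PR cut is stated), its cells would hold about 6 to 19 patients.

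**4. Information lost by the cut, if the EF effect is linear.** The share kept is r², the squared correlation between EF and the indicator EF > 35; the loss is 1 − r².

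*By hand, EF uniform on 20-40:* p = 0.25, overall mean 30, mean above the cut 37.5. Covariance = 0.25 × 7.5 = 1.875. Variances are 400/12 = 33.3 and 0.25 × 0.75 = 0.1875. r² = 1.875² / (33.3 × 0.1875) = 0.56, a loss of 44%.

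*Other assumed distributions:*

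| EF distribution (assumed) | share above 35% | loss |
|---|---|---|
| Normal, mean 28, SD 5, truncated at 40 | 7% | 73-74% |
| Normal, mean 30, SD 6, truncated at 40 | 16% | 60-61% |
| Uniform 10-40 | 17% | 58% |
| Normal, mean 32, SD 6, truncated at 40 | 24% | 52-53% |
| Normal, mean 35, SD 5, truncated at 40 | 41% | 39% |

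(Paired values are for lower limits of 15 and 10.) Normals with mean 28-35 and SD 5-7 span 39-74%. At those limits the contrast is worth 126 × 0.61 = 77 down to 126 × 0.26 = 33 patients analysed on continuous EF. Untruncated normals with 5-50% above the cut give 36-78%.

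**5. What continuous EF could detect.** The SE of the slope is 2.4 / (√126 × SD of EF). At 80% power the detectable slope per 10 EF points is 10 × 2.8 × 2.4 / (11.22 × SD) ≈ 6.0/SD. For an EF SD of 4 to 7 this is about 1.5 to 0.9 ml/kg/min per 10 points. The continuous term is more efficient under a linear trend, but it also finds only a steep gradient.

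**The case against.** The strongest objection is that 35% is not an arbitrary cut. Section 4.1 admits patients with EF 36-40% only on a BNP or NT-proBNP condition, so item 7 compares two entry routes. For that question recruitment EF is the right variable, and visit 3 EF would no longer identify the route. This stands, and it is why the split should be kept and reported with its CI.

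Second, the loss depends on the assumed shape. Correlation is symmetric: if response really steps at 35%, a continuous term loses the same share relative to the cut. This also stands, and it argues for having both analyses. Visit 3 EF carries measurement error too.

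Third, section 8.1 leaves detailed methods to the SAP, and item 7 does not bar a continuous analysis. Items 1, 5, 6 and 8 are also group comparisons, and items 2 and 9 do not say that PR and BMI will be modelled continuously. That limits the weight of the point. But item 7 does fix the EF grouping and the PR stratification, and an SAP that follows it would inherit both.

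A reader might infer that the trial throws away a known fraction of its EF information, or that the loss figure includes the age of the EF report. The documents support neither: they give no EF distribution, and the figure concerns the cut alone. Nor is the PR part of item 7 redundant, because item 2 covers peak VO₂ and haemodynamic response while item 7 extends to the secondary endpoints.

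**Conclusion.** The point holds as a modest improvement to one exploratory analysis. As written, item 7 is a reasonable entry-route comparison but a weak test of whether EF modifies response. Under a linear EF trend and the assumed distributions (7-41% of patients above 35%), the cut loses about 39-74% of the information. The exact limits are assumptions, but a loss of more than a third holds throughout the range examined. Without assuming any shape, the contrast detects only 1.3-2.0 ml/kg/min at 80% power if 10-30% of patients exceed 35%. A null result should therefore not be read as absence of an EF effect, and a positive one could not be separated from BNP selection. The primary analysis and the sample size are unaffected.

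**What to change.** In item 7 (or in the SAP section that carries it out):

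- Keep the recruitment split at 35%, label it an entry-route comparison, and report the between-group difference with its 95% CI.
- Add a treatment-by-EF interaction to the two-level model already specified in section 8.2, with EF continuous and taken from the visit 3 pre-randomisation echocardiogram.
- Enter PR interval as a continuous treatment interaction instead of stratifying within the EF groups.
- Report the change in treatment effect per 5 EF points with a 95% CI, and check linearity, for example with a spline plot.

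This takes a sentence or two of wording and needs no new data, visit or procedure. The price is a linearity assumption, which can be checked, and one more exploratory analysis in a list of nine. The added term will itself detect only a steep gradient, so its interval should be read as well as its p-value.

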3 STUDY DESIGN

3.1 Design

This is a multi-centre, prospective randomised double-blinded cross over study, recruiting a sub-population of patients with heart failure from multiple investigational sites in the UK. Recruitment is expected to take place over about 2 years.

All patients will be implanted with a Pacemaker or Implantable Cardioverter Defibrillator with one of the leads positioned on the His bundle in order to obtain His-bundle capture. There will be a 2-month run-in period where the device will be programmed not to deliver His pacing therapy during this period. Patients will be allocated in random order to six month treatment periods in each of the following two states (1) No His bundle pacing; (2) AV optimised Hisbundle pacing. Endpoint measurements will be taken at baseline, 6 months and 12 months post randomisation. Treatment allocation will be blinded to the endpoint assessor.

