5.3 Treatment

Patients entering the study will then attend for implantation of their device, this will be performed either at their local hospital or at Imperial College NHS Healthcare Trust, no later than 4 months of the patient's screening visit

Prior to implantation, blood tests will be performed to assess clotting function, full blood count and electrolytes. Additionally, blood will be taken for group and save if required as per local clinical practice. Antibiotic prophylaxis, analgesia and sedation can all be given as per the implanting institution's local policies and normal practice. As is standard clinical practice for pacemaker implantation, the following routine blood tests will be performed: creatinine level, haemoglobin level, prothrombin time (PT; clotting), and Group and Save (G+S). Tests performed up to a specified date prior to the implantation day can be accepted, please refer to Appendix 2 for details.

All patients will be implanted with a Pacemaker or Implantable cardioverter defibrillator (ICD). In all patients, a pacing lead will be positioned in the right atrium (typically the right atrial appendage). All patients will have a pacemaker lead positioned on the His bundle in order to obtain His-bundle capture. If it is not possible to successfully implant a His-bundle lead with selective His bundle capture or non-selective capture with < 40ms prolongation of the QRS duration, then a lead will be implanted in a lateral branch of the coronary sinus.

In patients who do not have an indication for an Implantable cardioverter defibrillator (ICD), a second ventricular lead will be implanted in a lateral branch of the coronary sinus. If His pacing has not been successfully achieved then a further lead will be positioned at the RV apex. In patients who do have an indication for an Implantable cardioverter defibrillator, the ICD lead will be positioned in the right ventricle (either RV apex or RV septum).

A chest X-Ray will be taken after the procedure to ensure the pacemaker leads are in position.

AV delay optimisation: will be performed using acute non-invasive blood pressure acquired using the Finometer device (Finapres Medical Systems, Netherlands). The BHF alternation protocol we have previously described will be used in order to minimise the effect of background noise ²².

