8 STATISTICAL ANALYSES

8.1 Sample Size and power considerations

We will use a smoothed modified Bruce protocol for patients with heart failure. This enables improved reproducibility of peak VO₂³⁰. With this approach, reproducibility in heart failure patients between two separate visits to the hospital is 2.4 ml/kg/min, expressed as the standard deviation of the difference between two independent measurements³¹. Implantation of a cardiac resynchronisation therapy pacemaker in patients with broad QRS duration and heart failure results in a 0.5-2.5 (mean 1.5) ml/kg/min increase in peak VO₂³²⁻³⁷. Our published pilot data is that switching on classical cardiac resynchronisation therapy in patients with a broad QRS duration increments LV systolic blood pressure by ~10.3mmHg, and switching on direct His-bundle pacing in long-PR/narrow-QRS patients increment blood pressure by ~6.3mmHg, i.e. ~60% of that effect. Pro-rata we would therefore expect an estimated increment in peak VO2 of 60% of 1.5ml/kg/min, i.e. 0.9 ml/kg/min.

Adopting a conservative approach, a two-sided alpha of 0.05 is chosen. Using a paired ttest, in order to detect a difference of 0.7 with SD of 2.4, to achieve a power of 90% would require a total of 126 evaluable patients. Allowing for a combined mortality/dropout of 21%, the study would require a total sample size of 160 patients. Consequently, 160 patients will be randomised in a 1:1 manner to the treatment groups.

Detailed analysis methods will be documented in the study's Statistical Analysis Plan (SAP).

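### Item 9 relates BMI to a peak VO2 change measured per kg, so if pacing helps, an inverse association can arise from scaling alone; report ml/min beside it

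*Protocol*

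**What the plan says.** Item 9 of the sub-group list in Protocol 8.2 (iv) asks for the "relationship between pacing device effect (in terms of change in peak VO2 and haemodynamic response) and BMI". It names no unit, model or test.

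The only unit the protocol gives for peak VO2 is in 5.5: "Exercise capacity will be measured as peak exercise oxygen consumption in ml/kg/min". Section 8.1 plans in the same unit, with a target "in order to detect a difference of 0.7 with SD of 2.4" and an expected gain of "60% of 1.5ml/kg/min, i.e. 0.9 ml/kg/min".

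The haemodynamic half of item 9 rests on a different measure. Under 5.3, AV delay optimisation "will be performed using acute non-invasive blood pressure acquired using the Finometer device", and blood pressure has no weight divisor.

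The effect is a within-patient contrast, because 3.1 states: "Patients will be allocated in random order to six month treatment periods in each of the following two states".

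**The concern.** Peak VO2 per kg is absolute uptake divided by weight, and BMI is weight divided by height squared. Weight therefore enters the outcome as a divisor and the predictor as a numerator. In item 9 the candidate modifier is built from the outcome's own denominator.

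Suppose pacing adds the same ml/min to every patient. Per kg, heavier patients then show a smaller change, and the analysis would show a downward slope against BMI. It would be easy to report this as heavier patients responding less, although their gain in oxygen uptake is the same. What is at stake is the wording of one exploratory sub-group statement. The primary comparison is not involved.

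**Working it through.** **The protocol's own figure.** Section 8.1 uses a paired t-test in which "a two-sided alpha of 0.05 is chosen", and says that "to achieve a power of 90% would require a total of 126 evaluable patients". The normal approximation gives (1.96 + 1.2816)² × 2.4² / 0.7² = 123.5, so 124. With the noncentral t distribution the smallest n is 126 (power 0.901). Allowing for 21% loss, 126 / 0.79 = 159.5, so 160. Both stated figures reproduce. I use n = 126 and SD 2.4 below.

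**The coupling.** Let A be a patient's on-off gain in ml/min, w weight and h height. The per-kg change is A / w = A / (BMI × h²).
- At equal height and equal A, the change at BMI 35 is 25/35 = 0.714 of that at BMI 25, a 29% fall.
- A gain worth 0.7 at BMI 28 reads 0.7 × 28/25 = 0.78 at BMI 25 and 0.7 × 28/35 = 0.56 at BMI 35.
- In weight terms, 0.7 × 85 = 59.5 ml/min reads 0.99 at 60 kg, 0.70 at 85 kg and 0.50 at 120 kg.

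**Size against the noise.** The documents give no BMI or height distribution. Assumptions: BMI mean 29, SD 5; height mean 1.72 m, SD 0.09; reference weight 85 kg; A proportional to w^b; a linear regression of the per-kg change on BMI. There were 2,000 simulated trials per row, with noise SD 2.4 on the per-kg scale.

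| Gain at 85 kg (ml/kg/min) | b | Mean slope per BMI unit | Mean r | Rejection at 5% |
|---|---|---|---|---|
| 0 | any | about 0 | about 0 | 4.1–4.7% |
| 0.7 | 0 (same ml/min) | −0.027 | −0.055 | 8.9% |
| 0.7 | 0.5 | −0.013 | −0.027 | 5.7% |
| 0.7 | 1 (same per kg) | −0.001 | −0.002 | 4.8% |
| 0.9 | 0 | −0.035 | −0.072 | 13.1% |
| 0.9 | 0.5 | −0.018 | −0.036 | 6.4% |
| 0.9 | 1 | 0.001 | 0.002 | 5.5% |

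**Check by hand for b = 0.** The noise-free slope is −0.026 for a gain of 0.7, so r is about −0.026 × 5 / 2.4 = −0.054. The shift of the test statistic is about 0.054 × √126 = 0.61, which gives a two-sided rejection rate near 9%. For 0.9 the slope is −0.0335, r about −0.070, the shift 0.78 and the rate about 12%.

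**Sensitivity.**
- With BMI mean 28, SD 5 and b = 0, the rates are 9.6% (0.7) and 12.6% (0.9) with noise per kg, and 11.2% and 12.9% with noise in ml/min.
- With noise in ml/min, the no-effect rate is 5.3 to 7.5% (BMI 29). Dividing by weight makes the variance unequal, but the mean slope stays at zero.
- For b = 0, roughly 91 to 98% of the significant results are inverse.
- If pacing harms (−0.7, b = 0), the slope turns positive, to +0.026.

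**The other scale.** Regressing the ml/min change on BMI rejects in about 5% of trials when the ml/min gain is constant. When the per-kg gain is constant, it rejects in about 8 to 12%, mostly with a positive slope. With a gain proportional to the square root of weight, both scales reject in about 6 to 9%.

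**The case against.** A reader might infer that the pairing of units guarantees a false inverse association. The documents do not support that. The outcome is a difference between two states in the same patient, so with no pacing effect the divisor changes the variance but leaves the expected slope at zero. The slope is also zero if the ml/min gain is proportional to weight, and positive if pacing harms. An inverse slope needs a real benefit that rises less than in proportion to weight. Even then it is a true statement on the per-kg scale, and misleads only when read as a smaller physiological response.

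A reader might also infer that ml/min is the correct scale. The constant-ml/min scenario is an assumption; the protocol's planning figures are per kg. Under a constant per-kg gain the ml/min analysis has the mirror-image bias. This objection stands, and it rules out replacing one scale with the other.

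It can also be said that item 9 is one of nine exploratory items, that half of it concerns blood pressure, and that unit and model belong in the SAP. The first two points stand and limit the weight of the finding. The third stands in part: the SAP, not available here, may already deal with this. But the protocol itself fixes the unit and names the modifier, and offers no other scaling of peak VO2.

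**Conclusion.** The concern holds in a limited form. For the peak VO2 part of item 9, an inverse association with BMI can come from scaling alone if pacing has a benefit that rises less than in proportion to weight. In the extreme case of an equal ml/min gain, the rejection rate roughly doubles, from 5% to about 9 to 13%, with a correlation of only about −0.06 to −0.07. Under intermediate scaling it is close to nominal, about 6%. These sizes rest on assumed BMI and height distributions and on a simple linear regression, none of which the protocol states. The zero slopes under no effect or a proportional gain do not depend on the assumed distributions. Neither scale is neutral, so an association seen on one alone cannot be read as effect modification. The haemodynamic part of item 9, the primary analysis and the sample size are untouched.

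**What to change.** In item 9, or in the SAP before database lock, specify that the BMI relationship for the on-off change in peak VO2 is reported both in ml/kg/min and in absolute ml/min, with estimates and confidence intervals side by side and neither labelled as the main result. Interpret BMI as modifying the response only if the direction is the same on both scales. A gain that scales anywhere between constant and proportional to weight gives expected slopes that are zero or of opposite sign on the two scales, so agreement asks for more than scaling. It is a minimum condition, not independent confirmation, because both analyses use the same tests.

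No new measurement is needed: absolute uptake is the per-kg value multiplied by the weight used for that test. The primary endpoint stays in ml/kg/min. The cost is one extra exploratory analysis and a more cautious reading of an association that appears on one scale only.
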